# Deception and Debriefing

**Only complete the sections below if requesting an alteration of informed consent that involves deceiving research participants.** If this study does not involve deception, skip to 35.

See IRB Policies and Procedures Section 15 for a description of deception.

Click on the check box (or double click and type an "X" if using Google Docs).

- **32** It is appropriate to provide additional pertinent information to the subject after research activities are complete (e.g., the researcher needed to deceive to subject to the nature of the study).
- **33** Research participants will have the opportunity to withdrawal their data during the debriefing.
- **34** Describe the nature of deception and why it is necessary to conduct the research. *To input text, click in the light grey area below.*
- **35** Describe debriefing procedures. *To input text, click in the light grey area below.*

# BENEFITS

#### **36** Benefits to Society

Describe the scientific and societal benefit(s) below.

#### To input text, click in the light grey area below.

We hypothesize that providing empathetic and relationship-oriented telephone calls by lightly trained lay persons can support diabetes self-management behaviors and reduce Hemoglobin A1c. By measuring the impact of such a lay person driven program on Hemoglobin A1C and mental health we plan to build a case for the health system to pay for better outcomes through such programs and influence the development of a novel workforce.

**Benefits to Participants** 

*Click on the applicable check box (or double click and type an "X" if using Google Docs).* 

- **37** There is no anticipated direct benefit to participants.
- **38** There are anticipated benefits to participants.
- **39** If applicable, describe the potential direct benefits to participants. *To input text, click in the light grey area below.* 
  - Participants in the intervention arm will receive phone calls that may make them feel better by having someone listen and empathize with them.

# RISKS

# **40** Describe the risks associated with each activity in this research *To input text, click in the light grey area below.*

- Finger stick blood sample for HbA1c blood testing: The risks of obtaining a blood sample are minimal, similar to any time blood is collected and include pain, bleeding, bruising, infection, and skin irritations (from cleaning agents used to sterilize the skin or bandages).
- Blood Pressure: Participants may experience mild discomfort in their arm when the cuff is inflated.
- Loss of confidentiality: There is a potential for accidental release of confidential information. Procedures are in place to minimize this risk.

# 41 Describe how each risk is mitigated/minimized.

To input text, click in the light grey area below.

- Study team members collecting BP and blood samples will be trained on proper technique to maintain safety and minimize discomfort
- Participant study numbers and a secure REDCap database will be used to protect patient confidentiality.

# Data Safety Monitoring

For additional information regarding data safety monitoring boards and data safety monitoring plans, please see Section 21 of our Policies and Procedures.

*Click on the check box (or double click and type an "X" if using Google Docs).* 

- **42** In this study is minimal risk and does not require a Data Safety Monitoring Plan (DSMP) or a Data Safety Monitoring Board (DMSB).
- **43** This study does not have a Data Safety Monitoring Board, but researchers have an internal plan/policy to monitor for safety. *Complete Data Safety Monitoring Details (44-51).*
- 44 This study has a Data Safety Monitoring Board (DSMB). Complete Data Safety Monitoring Details (44-51) or upload this study's Data Safety Monitoring Board's charter.

# Data Safety Monitoring (Details)

#### **45 How is safety information collected?** *To input text, click in the light grey area below.*

# 46 When will safety data collection start (for each participant or for the whole study, as applicable)?

To input text, click in the light grey area below.

#### **47** How frequently will safety data be collected? *To input text, click in the light grey area below.*

48 Who will review the data for safety? To input text, click in the light grey area below.

49 How frequently will data be monitored for safety concerns? To input text, click in the light grey area below.

- 50 What data will be reviewed? To input text, click in the light grey area below.
- **51** State the frequency or periodicity of the review of cumulative data? *To input text, click in the light grey area below.*
- **52** State any conditions that would trigger an immediate suspension of the research. *To input text, click in the light grey area below.*

#### Early Withdrawal

**Only complete this section if there are planned conditions under which a participant will be withdrawn from the study.** If not applicable, skip to 56.

Include this information in your consent form.

53 List the criteria for withdrawing individual participants from the study (e.g., safety or toxicity concerns, emotional distress, inability to comply with the protocol, or requirements from study sponsor).

To input text, click in the light grey area below.

Participants may be withdrawn from the study if they verbally abusive or inappropriate with callers.

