#### To input text, click in the light grey area below.

Design: Randomized controlled trial.

**Population**: Adults with Hemoglobin A1C >8.0 measured at any point in the 12 months prior to enrollment, who have had at least one visit (Family medicine, behavioral health or other) with Lone Star Circle of Care within the past 12 months (in person or telehealth)

**Randomization:** Consented participants will be randomized to the intervention or control arm in a 1:1 ratio.

[figure not shown]
**Blinding:** Research staff involved in taking biomedical measurements will be blinded to participant status. Participants will complete surveys in person using a tablet or individual paper copy, thus research associates will remain blinded.

Time period: The study is divided into two parts.

- *Phase 1 (6 months)* is a randomized controlled trial testing the effect of telephone call-based empathetic engagement supported by caller-customized letters, together with small self-selected incentives (health tool) and caller-selected personal recognitions (small gifts selected based on the callers understanding of the participant), and low-literacy basic diabetes self-management information, against usual care. The primary outcome is Hemoglobin A1C (A1C) with repeated measures at baseline, 3 and 6 months.
- *Phase 2 (subsequent 6 months)* is the follow-up phase allowing us to *estimate* the 12 month longer term trajectory of A1C in Intervention and Control. To maximize the utility of the study to inform the most effective program design, participants in the control arm will receive the same opportunity to self-select health tool as the intervention arm received in Phase 1, but will make the choice during the 6

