- Choice of a health-promoting tool offered as one of the final questions of the 6 month assessment. A choice will be provided at the end of the 6 month surveys between a pedometer and a smart weigh scale of equivalent value. If neither of these options are applicable based on health or other limitations, back-up options will be offered to them (fitness resistant bands or exercise program for upper body fitness). The tool will be mailed within the 7th month.
- A choice 2 items from the same set of items used for the Intervention arm in Phase 1 related to healthier living, each <\$25/-. This will be offered as one of the final questions of the 6 month assessment. The selected items will be mailed out to the participant in the 8th month and 10th month.
- Participants in the control arm do not receive the communications elements, telephone calls or letters, and otherwise continue with their normal standard of care.
- Participants in the control arm do not receive any text messaging reminders related to the program. To prevent loss to follow-up in the control arm, we will send research study reminder text messages about upcoming measurement appointments.

**Measures:** Primary outcome is Hemoglobin A1C at 6 months (repeated measures at 3 and 6, 9 and 12 months). The measurements will be taken at Lone Star clinic sites, Dell Medical School at The University of Texas at Austin, or other community-based sites, by a member of the research team. Secondary outcomes include Blood pressure through direct measurement and self-reported depression (PHQ-9), anxiety (GAD-7), general mental and physical health (SF-12) and self-reported healthcare utilization and will also be measured at Lone Star clinic sites, Dell Medical School at The University of Texas at Austin, or other community-based sites, by a member of the research team. In addition, process measures include measurements directly from the telephone call system: calls placed/attempted; calls connected (someone spoke); call duration. See below for table of all measures and method of collection.

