#### b. Consent

- i. Interested participants will be called by study staff to screen and share consent information. Consent will then be signed electronically, through DocuSign, or for those that do not complete this, the first time they come to a clinic site, Dell Medical School at The University of Texas at Austin, community-based site, or on rare occasion in people's homes, for baseline measurement, they will sign in person. No research activities will take place before informed consent is completed.
- 2. Measure collection
  - a. General: Research associates/study staff will collect biomedical measures. Participants will fill out their own surveys on iPads/tablets at the measure collection site. Paper copies will be available for participants to complete upon request. Research associates will be blinded to the status of the participants.
  - b. First measure collection
    - i. After phone screening and consent, the participant will be invited to come the clinic site, Dell Medical School at The University of Texas at Austin, other community-based site, or on rare occasion in people's homes on weekends and/or in the evenings and given choices on when to schedule measurement collection. When they come to the site, they will get a chance to sign consent forms if they haven't done so electronically; then study staff will collect A1C and blood pressure measurements. After this, participants will use a tablet or paper copy to answer survey information. The survey

information will be saved directly into a RedCap database. The paper copy of the responses, if used, will be stored in a locked cabinet.

- c. Subsequent measure collections (3, 6, 9 and 12 months)
  - i. Similar to above, without informed consent process.
  - ii. The program improvement survey, administered at the 12-month (last) measurement visit will only be collected once, during the 12month visit. It will be collected from intervention participants only via the electronic tablet where all other measures are answered.
- 3. Randomization
  - a. To ensure that the effect of the empathy calls program can be assessed without confounding it with depressive mood, we will rely on stratified randomization so that approximately 50% (N=75) of the individuals in both the control and experimental group have a PHQ9 > 5 at baseline and 50% of the individuals have PHQ9 < 5 at baseline. Randomization will occur after participant consent and collection of baseline measures.
- 4. Program Intervention

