  - a. Intervention arm
    - i. After the participant has been randomized into the intervention arm, they will be allocated to a caller's panel by an unblinded program manager. Each caller has a panel of anywhere from 10-25 participants. Callers will place the first call within 1-5 days of receiving the name of a participant. Callers will use an app on their phone to be reminded of the schedule of calls and to initiate calls such that basic metrics can be collected (e.g., the call occurred, call duration, etc). Calls are not recorded.
    - ii. First week of the program: Choice of a health-promoting tool offered by the caller in the first week of the program. A choice will be provided by the caller between a pedometer and a smart weigh scale of equivalent value. If neither of these options are applicable based on health or other limitations, back-up options will be offered to them (fitness resistant bands or exercise program for upper body fitness). The chosen health-promoting tool will be mailed out by the 5th week of the program. Low-literacy diabetes self-management information will also be mailed out after randomization occurs.
    - iii. Month 2-5 of the program: Callers will select 2 items, one by Month 2.5 (7 weeks in), and one by Month 4.5 (18 weeks in), and the program will mail these items to participants as personal recognitions of the participants managing diabetes in their life. The

items will each be of <\$25.00 value, will come from a pre-selected list of items that are related to the main levers of diabetes selfmanagement, nutrition, activity, sleep and med adherence. Callers will be allowed to add to the pre-selected list if they identify something they think will be particularly well-received by the participant but isn't on the original list. That item will then become part of the super set of items that other callers can choose from. Examples of items include cookbooks, blender, children's cooking kit, spices, meal kits, gear to hold iPod and headphones while exercising, etc.

[figure not shown]

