  - Weeks 2-4: 50 minutes or less per week
  - Months 2-6: 10 minutes or less per week
- b. Control arm
  - i. Program Phase (Months 1-6): Control participants will receive their usual care during the first 6 months of the program.
  - ii. Follow-up Phase (Months 7-12): Through a survey at the end of the 6-month assessment, control participants are provided the same health tools and 'gift' options as the intervention arm was at the beginning of the program phase. They are provided a choice between a pedometer and a smart weigh scale (if neither of these options are applicable based on health or other limitations, back-up options will be offered to them (fitness resistant bands or exercise program for upper body fitness)); and they are provided a choice between the same set of items, each <\$25.00 and all related in some way to eating better, exercise, sleep or tools to help remember to take medications. The health tool and diabetes selfmanagement information is delivered via mail on the same schedule as the intervention participants. The gifts selected by control participants will be mailed in Month 2 and Month 4.
  - iii. Time commitment for control measurements same as for intervention, see above.
  - iv. Time commitment for control intervention none.

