# 54 Describe any necessary procedures for ensuring the safety of a participant who has withdrawn early.

To input text, click in the light grey area below.

There are no procedures in place to ensure the safety of a participant that is withdrawn for abusive or inappropriate behavior toward callers. This is a minimal risk study and being withdrawn poses no risk to the participant.

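### The withdrawal rule for conduct toward callers can remove participants from the intervention arm only, and the plan does not say that their outcome visits continue

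*Combined protocol and SAP*

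**What the plan says.** Item 53 gives one criterion for withdrawing a participant: "Participants may be withdrawn from the study if they verbally abusive or inappropriate with callers". Item 54, on what follows such a withdrawal, deals only with safety: "There are no procedures in place to ensure the safety of a participant that is withdrawn for abusive or inappropriate behavior toward callers". Neither item says whether outcome measurement continues.

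Contact with callers exists in one arm only:
- Item 11, step 3: "Randomization will occur after participant consent and collection of baseline measures".
- Item 11, step 4a: "After the participant has been randomized into the intervention arm, they will be allocated to a" caller's panel.
- Item 4, Control: these participants do not "receive the communications elements, telephone calls or letters, and otherwise continue with their normal standard of care".
- Item 11, step 4b: "Control participants will receive their usual care during the first 6 months of the program".

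Outcomes do not depend on the calls. Items 4 and 11 have A1c and blood pressure taken at in-person visits by research staff blinded to arm, with surveys completed at the same visits, at baseline and at 3, 6, 9 and 12 months.

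Item 5 analyses A1c with a linear mixed model. It defines no analysis set and gives no method for missing data.

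On reminders, item 4 says under Control: "To prevent loss to follow-up in the control arm, we will send research study reminder text messages about upcoming measurement appointments". The texts described for the intervention arm concern upcoming calls and, in months 7-12, tips discussed with the caller.

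**The concern.** Randomisation makes the arms comparable at baseline, and that comparability lasts only while outcomes are sought equally in both. Here the protocol itself creates a route out of follow-up that no control participant can take. It is triggered by behaviour during the intervention and left to discretion with no stated threshold. If the people removed would have had different A1c from those who stay, the arm difference shifts.

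The loss is also unnecessary. The behaviour concerns callers, while the visits are run by other staff. An A1c value that was never collected cannot be recovered at analysis.

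**Working it through.** **1. Can a control participant meet the criterion?** The rule requires conduct toward a caller. Callers are allocated after randomisation, in the intervention arm. Controls receive no calls. The answer is no, so the asymmetry is built into the design.

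**2. What is lost?** Calls run through months 1-6, so the rule operates in that period. Visits before the withdrawal are kept: someone withdrawn after the 3-month visit still has a baseline and a 3-month A1c. On the plain meaning of leaving the study, later visits are lost, normally including month 6, the primary time point.

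**3. Effect on power.** Item 5 states that 150 per arm, three assessments, a correlation of .30 and alpha .05 give 80% power at f = .09 and 90% at f = .10. For the group-by-time interaction in repeated-measures ANOVA (sphericity assumed), take lambda = f² × N × m / (1 − r), with N = 300, m = 3, r = .30 and degrees of freedom 2 and 596. The minimum detectable f is 0.0868 at 80% and 0.0995 at 90%, which round to the stated figures. Power at exactly f = .09 is 0.830, and at f = .10 it is 0.903.

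For w withdrawals in the intervention arm, replace N by 4 × n1 × n2 / (n1 + n2), with n1 = 150 − w and n2 = 150. For w = 15 this is 4 × 135 × 150 / 285 = 284.2.

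**4. Effect on the estimate.** Let p be the share of the arm withdrawn and d the difference in mean 6-month A1c, withdrawn minus retained. The full-arm mean is the retained mean plus p × d. Using the retained mean alone is therefore off by p × d. Both p and d are assumptions, since the documents give neither.

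- p = 1% of 150 (1.5 people), d = 1.0: 0.01 × 1.0 = 0.01 points.
- p = 5% of 150 (7.5 people), d = 1.0: 0.05 × 1.0 = 0.05 points.

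A wider range:

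| w of 150 | Power at f = .09 / .10 | Bias if d = 0.5 | d = 1.0 | d = 2.0 |
|---|---|---|---|---|
| 0 | 0.830 / 0.903 | 0 | 0 | 0 |
| 3 | 0.826 / 0.900 | 0.01 | 0.02 | 0.04 |
| 8 | 0.819 / 0.895 | 0.03 | 0.05 | 0.11 |
| 15 | 0.808 / 0.886 | 0.05 | 0.10 | 0.20 |

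Power falls by about 2 points even at w = 15, so bias is the issue. For scale, item 2 cites a reduction of 0.8 in an earlier telephone programme among those starting above 9%. A bias of 0.05 is 0.05 / 0.8, or about 6% of that.

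**5. Does the mixed model repair it?** In part, perhaps. It uses baseline and 3-month A1c, so it can recover what those values predict about month 6. It does not recover a difference unrelated to observed data. Item 5 also includes change in PHQ-9 from baseline to month 6 as a covariate, which is undefined for anyone who leaves before month 6. Without a missing-data rule, such a person's 3-month A1c could drop out too. That covariate is a separate problem affecting both arms, and is not counted in the figures above.

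**The case against.** The strongest reply is that this is a discretionary rule likely to touch very few people. No rate is given, and the upper corner of the table needs a tenth of the arm withdrawn for misconduct together with a 2-point gap, neither of which the documents suggest. That stands, and it keeps the point small.

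The wording may also come from the form, whose item 53 prompt itself speaks of withdrawing participants from the study. The section asks for the same information in the consent form, which was not available to check. This is fair: the sponsor may intend only to stop the calls. But the text as it stands says otherwise, and no other section corrects it.

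Continued visits mean continued face-to-face contact, occasionally in homes. That is a real cost, and the fix needs an exception for staff safety.

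Two stronger readings are tempting, and the documents do not support them:
- A reader might infer that A1c at 3, 6, 9 and 12 months is all lost. Only visits after the withdrawal would be, and even that follows from the plain meaning of the rule rather than an explicit statement.
- A reader might infer that intervention participants get no appointment reminders. The sentence on reminders follows one saying that controls get no programme-related texts, and it explains which texts they do get. It is silent on the other arm. Nor would the two provisions offset each other: if only controls were reminded, that too would lower retention in the intervention arm relative to control.

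**Conclusion.** The point holds as a one-sided rule that should be changed. Item 53, read as written, permits loss of outcomes in the intervention arm alone, on post-randomisation behaviour, and nothing in the plan keeps these participants in follow-up or states that all are analysed as randomised.

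The likely size is about 0.01-0.05 A1c points before any adjustment by the model. This rests on 1-5% withdrawn and a 1.0-point gap, both assumed. A reader might go further and conclude that the trial is biased toward benefit. The documents do not show that, because nothing in them links conduct on calls to A1c. The bias runs that way only if those withdrawn do worse, and with no gap it is zero.

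The reminders are a secondary point, to be confirmed rather than counted as an error.

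**What to change.** Whatever rule the sponsor keeps for ending calls, reword item 53 and the matching consent text so that ending calls does not end study participation. State that these participants are invited to all remaining measurement visits, unless they withdraw consent or their conduct at visits makes this unsafe for staff. In item 5, state that they are analysed in their randomised arm. If their outcomes are collected, this source of bias disappears. The change should be made before any such withdrawal occurs.

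In item 4, state whether both arms receive the same measurement-appointment reminders; if they do not, send them to both.

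The cost is a protocol and consent edit, continued in-person contact with a few difficult participants and, if reminders are now limited to controls, texts to 150 more people. The visits themselves are already planned and compensated.
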